## 9.0 Procedures Involved

- 9.1 We will conduct a randomized trial using a 2x2 factorial design to test the effectiveness of UMS interventions to improve safe use and adherence to complex prescription (Rx) regimens. The research will be performed at Erie Family Health Center clinics and Northwestern Memorial HealthCare (NMHC) in Chicago.
- 9.2 **Research Coordinator Training.** The RCs and the project manager will contact and consent participants, conduct interviews, perform retention and follow-up activities and quality assurance. All have completed human subjects training (CITI) and intensive training from [name] in interview protocols and safe data transfer. They also have multiple years of patient interviewing and data management experience. Simulations will be used to monitor interviewer proficiencies. Our staff has ample experience conducting surveys measuring medication-related outcomes.
- 9.3 **Computer Programming.** We will be using RedCap to collect all data. This allows for straightforward electronic entry of participant responses by the RC and generation of data files compatible with statistical programs. The database is both encrypted and password protected, and is only accessible by approved study personnel at Northwestern. [name] (analyst) will oversee the database structure and quality assurance activities.
- 9.4 **Data Safety and Monitoring Board (DSMB).** The DSMB will be formed early in the project and be given responsibility to review and approve the methods and analysis plan. It will be organized by Drs. [name] and [name] and include 4 health services researchers with related expertise. Meetings will be via video/tele-

conference to review protocols, procedures, and concerns related to research integrity.

9.5 **Trial Registration.** This study is registered at ClinicalTrials.gov (NCT02820753).

9.6 **Implementation and e-bugging of EHR, Portal Tools.** [name] will plan the implementation of the EHR tools within the GE Centricity EHR with [name] (Alliance CEO), [name] and [name]. All have considerable experience implementing changes to this system. [name] has implemented the same processes to be tested in this study within Epic and Cerner platforms. Alliance's informatics analysts will implement the EHR and portal tools, assist with piloting in the electronic test environment, troubleshoot and communicate with GE Centricity if necessary, and roll out tools to Alliance sites. Drs. [name], [name] and [name] and [name] will work together to impart the specific functionality (portal survey and electronic views of Medlist, Medsheet) on the Alliance portal, as well as ensuring functionality of the lab reports to the clinic containing the portal survey results. [name] will also work with Epic programmers at NMHC to refine the build in Epic for Northwestern clinics. While all functions have already been programmed at Northwestern, some functions may need to be tweaked and turned on accordingly.

9.7 **Randomization.** Randomization will occur at the patient level. Patients will be randomized to 1 of 4 arms (1:2:2:2). Because all arms receive the EHR tools, we are able to 'turn on' those features at all participating clinics. The other interventions occur outside of the clinic setting, so we are able to assign patients to those arms at an individual level.

9.8 **Clinic Space, Orientation and Workflow.** Prior to implementation, [name] will meet with physicians and staff at each of the sites to familiarize them with the planned study activities, answer questions, provide a printed synopsis of the protocol per site, and give contact information. They will work closely with [name] to coordinate activities at the sites and plan space needs for interviews and study visits.

9.9 **Spanish Translation.** All of the measures identified already have Spanish versions. We will employ [name], from Research Support Services, to translate remaining components (introduction prompts, item probes, surveys, etc.), as well as the consent and recruitment materials into Spanish. [name] has specialized in research studies with Hispanic populations, including topics such as methodology for instrument translations and qualitative pretesting of survey instruments in Spanish, since 1984 and we have worked with her extensively. [name] (Spanish) will review all materials and facilitate any discussion to reach an agreement on the best words and phrases for the final product.

9.10 **Pilot-testing and Refinement of Study Materials and Protocol.** We will pilot-test the study battery, protocol and patient materials among English and Spanish-speaking patients at Alliance sites. Cognitive interviews will be conducted among a convenience sample of 30 patients (n=15 per language) that meet eligibility criteria to refine and standardize the study materials. We will 1) obtain average completion times for the interview and 2) elicit patient comprehension and acceptability of the interview and patient materials through a set of targeted questions. If problems are

identified, the root cause(s) will be analyzed and modifications made to the interview and materials as appropriate prior to full-scale implementation.

**9.11 Interviews.** The initial interview will be conducted in person or over the phone at the time of patient consent and enrollment. Following the baseline interview, RCs will conduct one telephone interview 6-8 weeks later. Assessments at this interview are aimed to closely track any change in the most proximal outcomes of Rx understanding and behavioral outcomes (self-report adherence). A final in-person interview or phone interview (if unable to complete in person due to NU COVID-19 in-person interview restrictions) will then be conducted 6 months post baseline. Patients will receive financial incentives to attend study visits (\$40 for baseline interview, \$60 at 6 months). In addition, patients will receive reimbursement for text messaging costs if they do not have unlimited texting = (estimated costs based on greatest possible incurred charge). Patients will be provided \$10 for transportation costs or a parking pass.

**★ COVID-19 Waves 5-9 Patient Interviews.** Participants will complete up to five telephone interviews in total, with one interview taking place every 4 months. New, supplement-specific data collection related to COVID-19 will be collected via telephone interviews. See section 9.20 for more information

**9.12 Obtaining Clinical Markers Data.** At in-person baseline and 6 months, trained RCs will use a blood pressure monitor to measure systolic/diastolic blood pressure on all participants. RCs will use an automated, validated device (Omron HEM-907XL) and procedures used in the National Health Examination and Nutrition Survey (NHANES). RCs will ask patients to sit quietly with feet and back supported for 5 minutes before blood pressure is obtained. Three recordings will be taken per visit, spaced at least 5 minutes apart, and the mean of the 2nd and 3rd readings will be used to indicate blood pressure for that visit. Patient positioning, arm selection, cuff size selection and other techniques will follow NHANES procedures. Baseline and 6-month interviews that are completed over the phone will not obtain in-person blood pressure values.

In the event that a patient has a high blood pressure screening (systolic >180 or diastolic >110): For patients with a high blood pressure screening, the RC will proceed to the following Hypertensive Emergency Screening Questions:

**Hypertensive Emergency Screening Questions:**

Are you currently experiencing...

- Severe pain in the chest and/or upper back?
- Nausea or vomiting?
- New vision changes?
- Severe trouble breathing?
- A headache? (Must say yes to both sub-questions to count as a yes)

- Is it different from prior headaches?
- Is it severe?

The RC will then instruct the patients based on the following for Erie patients:

- For interviews done at an Erie site, and patient has a systolic >180 or diastolic >110: Patient should be transferred in real time to the on-site nurse for a full assessment and provider consultation regardless of responses to screening questions. The RC will provide the patient with their blood pressure values on a piece of paper.
- For interviews done at Northwestern, and patient has a systolic >180 or diastolic >110:
  - Patient should be advised to go to the Northwestern Emergency Department regardless of responses to screening questions before leaving the interview. The RC will provide the patient with their blood pressure values on a piece of paper.
  - The RC should notify Erie Family Health Centers of the patient's blood pressure screening and that the patient was advised to go to the Emergency Department
    - The RC should call Erie directly and follow the phone tree to speak with a Patient Access Representative, [contact]
  - Erie Staff will notify the patient's Primary Care Provider

The RC will then instruct the patients based on the following for Northwestern patients:

- If yes to any screening questions above, patient should either call their PCP's office from the interview room to speak to a healthcare provider for advice, or proceed to the ER.
- If no to all screening questions above, patient should be instructed to call their primary care doctor.

For diabetic patients, a chart review or EDW pull will be done to examine Hemoglobin A1c (hbA1c) levels at their regularly scheduled primary care appointments closest to baseline and 6 month interviews. This is to decrease the burden on the participant – alternatives include taking a blood sample at our interview or asking participants to go to Quest Diagnostics. We felt that was excessive and unnecessary, so will use the EHR data provided by Erie or the EDW report for Northwestern patients.

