### 7.1 Study Duration.

1. The anticipated duration of participation will be 6 months. Patients will complete an in-person or phone baseline interview after having a regularly scheduled doctor appointment. They will then complete a 6-8 week phone interview, and a 6-month post baseline, in-person interview or phone interview (if unable to complete in person due to NU COVID-19 in-person interview restrictions).
2. We have allotted 36 months to recruit and enroll all participants.
3. We anticipate 9 additional months to finish preliminary analysis. The estimated date to complete analysis is May 2021.

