RC can take a screen shot of the patient's remaining pills-per bottle. The RC will save the screen shot/photograph to the study project folder within the secure GIM server only using the patient's studyid to identify the photograph. No PHI will be captured in the photograph. If the participant does not have video capabilities, the RC will proceed to explain how the patient can count their pills and relay the number to the RC. This script is outlined in the interview script. For patients consented before May 19, 2020 that complete a phone 6 month, a brief script will be read informing patients of the change in the consent in regards to the pill count. The RC will ask the participant to provide verbal consent to allow the study team to take a screen shot/photograph of the patient's pills during a video call in order for the RC to count the pills after the interview. The patient will be notified that no PHI will be captured in the photograph.

**Medication reconciliation.** Chart reviews will determine whether any discrepancies are present between patient self-report and the chart medication list. Nature of the discrepancy (omission vs. commission) will be recorded.

**Clinical Outcomes.** Systolic/diastolic blood pressure will be collected on all patients during the baseline and 6 month interview. Low-density lipoprotein cholesterol (LDL) will be obtained from patients' electronic health records. Chart review of hemoglobin A1c (hbA1c) will be reviewed for all diabetic patients. Differences will be measured between the last clinical measurement prior to baseline assessment and the last measured value during the study period (closest to 6 month assessment).

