The UMS EHR tools have been piloted in Epic and Cerner, and are now being implemented in GE Centricity for this proposal now. Among 144 patients at the NMFF General Medicine clinic, nearly all (91%) patients received their MedList, UMS sigs, and MedSheets for new medications; 85% reviewed it with their doctor. Feedback from 20 physicians offered unanimous positive feedback on the tools. [R18HS17220].

**9.14 SMS Text Reminders.** For those patients receiving text reminders (SMS; SMS+Portal), daily text reminders will be sent post baseline following the UMS intervals. The texts will continue daily, with the option to opt out at any time. Stopping the texts will not impact their continuance in the study. Texts will automatically stop after 6 weeks, with an option at that time for patients to opt back in to the service. Those who opt back in will get the texts all 6 months of the study, or until they decide to stop. In past studies we have sent texts for one week, but recent studies have shown patients may benefit from longer text interventions. A covariate will be to look at the effect of length of text intervention to patient adherence, as well

as whether or not people opted out. Participants without unlimited texting plans will be reimbursed the total cost of receiving the texts. Patients will receive uniform, generic messages around UMS time intervals such as, “Good Morning! Please remember to take your medicines today.” and, “Hope you had a great day and remembered to take all your medicine!”

We will use EZ Texting, a safe, economical, premium Internet SMS text service plan, to program and schedule discrete UMS-centered text messages. These will be sent at standard intervals for all patients based on their regimen, with a maximum of two times a day (i.e. 1 or 2 times daily depending on regimen). Because these reminders are sent daily, we have limited the number of times sent per day so as not to burden and overwhelm the patient. Generic reminders are used due to the complexity of patient regimens and the SMS text message itself sent around the general time of behavior is a memory support. The premium plan ensures patients do not receive promotional messages with the text. A trained RC will orient and confirm patients can retrieve text messages. The RC will also instruct patients to abstain from reading text messages while driving and instead read messages and take medicines once they can safely concentrate on the task.

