**9.15 EHR Web-Based Patient Portal.** The addition of the patient portal will provide opportunities to have ongoing communications with their clinic, real-time reconciliation and updating of medication lists, access to regimen-specific medication information, and to provide a feedback loop informing healthcare providers of adherence-related behaviors and concerns. The encrypted patient portal website will be managed by the Alliance HIT team and the MyChart team, under [name] supervision. Secured instant messaging and email features to communicate with clinic staff are already available within the portal. The additional build out above these informational and communication features will be a periodic requests for patients to (1) identify if they missed taking any of the medicine in their regimen in the past 3 days, and (2) list any concerns or problems related to refill, cost, side effects, or management of their medicines. This process has previously been piloted with patients and can be performed in three minutes or less. Patients in this arm will be asked to fill this survey out 2 weeks, 1, 2, 3, 4, and 5 months post baseline. An email will be sent to patients at these time points, requesting that they access the portal and complete the regimen adherence assessment (embedded in the portal). The information submitted back by the patient will be sent back to the EHR and directed to the responsible doctor or nurse. Identified ‘champions’ at Erie and NMHC will be trained to review the files and identify patients with regimen-related concerns. Patients who do not complete the assessment within 48 hours will be sent a second email reminder. If they still do not fill out the survey, a third and final reminder will be sent. Patients who self-report any concerns or who demonstrate incorrect or missed doses will also trigger nurse follow-up. The RC will create a MyChart or MyErieHealth account for patients that do not already have a patient portal account, depending on the clinic they attend. For Erie patients, a MyErieHealth account will be created through the MyErieHealth admin page. For Northwestern patients, the RC will obtain a MyChart activation code by accessing a patient's chart through Epic. Erie staff will send encrypted emails weekly or as needed to NU RC's with a list of patients that have completed the portal survey. For Northwestern patients, RC's will

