  - Primary language
  - Date of last primary doctor appointment at Erie
  - All drugs prescribed (name, dose, form, GPI, instruction, date prescribed, number of refills, pharmacy, quantity)
- NU will send Alliance/Erie Family Health Center Study IDs and baseline interview dates, linked by patient ID
- Alliance will send the following information to Northwestern for consented patients:
  - Study ID
  - All values 6 months prior to baseline & 12 months post
    - Blood pressure
    - HbA1c
    - Cholesterol levels
  - Information on all prescribed medicines baseline to 12 months post (name, dose, form, GPI, instruction, date prescribed, number of refills, pharmacy, quantity)
  - Current at baseline and 12 months post
    - Chronic conditions
    - COVID-19 diagnosis and/or results of antibody test
  - All clinic visits/appointments 6 months prior to baseline and 12 months post (date, provider, meds prescribed, visit type)
  - Patient portal survey results, date completed, and possible clinic contact for patients in either of the portal arms
  - Patient portal use 6 months prior to baseline and 36 months post baseline
    - how many times patient logged on to portal
    - what portal was used for
    - when and how often portal was used

For Northwestern patients, the same data that was requested above will be obtained through an additional EDW report, including patient medications, chronic conditions, COVID-19 diagnosis and/or results of antibody test, and healthcare utilization (ED, hospitalization, primary care appointments) as well as hypertension, diabetes and cholesterol clinical values.

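### Sections 8.2 and 9.12 pick the HbA1c baseline by different rules, and 9.12 read literally allows a baseline value taken after the intervention has begun (minor)

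*Combined protocol and SAP*

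**What the plan says.** Section 8.2 (Clinical Outcomes) covers blood pressure, LDL and HbA1c and defines the change: "Differences will be measured between the last clinical measurement prior to baseline assessment and the last measured value during the study period". A bracket adds that the follow-up value is the one "closest to 6 month assessment".

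Section 9.12, on diabetic patients only, says that chart review or a data-warehouse pull will supply HbA1c from the routine primary care visits "closest to baseline and 6 month interviews". It gives no direction in time.

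Section 9.19 sets the extraction for Erie patients as "All values 6 months prior to baseline & 12 months post", with HbA1c in the list, and requests the same data for Northwestern patients.

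On timing, section 7.1 states: "Patients will complete an in-person or phone baseline interview after having a regularly scheduled doctor appointment". Section 3.1 likewise places screening after the visit. Under 9.14, "daily text reminders will be sent post baseline following the UMS intervals". Under 9.15, "Patients in this arm will be asked to fill this survey out 2 weeks, 1, 2, 3, 4, and 5 months post baseline". Section 22.1 also places the arm-specific components after the baseline interview. The exact moment of randomisation is not stated.

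The status of HbA1c varies. Section 8.2 carries a primary-endpoint heading, 11.1 (Aim 1) gives clinical outcomes secondary interest, and 11.1 (Exploratory Analyses) treats HbA1c as exploratory and warns of limited power.

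**The concern.** The two sections can select different values for the same patient, and nothing says which one prevails. The 8.2 baseline is strictly before the baseline assessment. The 9.12 baseline is not, and the extraction includes later values, so the nearest one may have been drawn once texts or portal surveys were running.

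A baseline that already carries some of the treatment effect is unsound both as the origin of a change score and as a covariate. The covariate use is a live possibility: section 11.1 examines baseline outcomes for balance and enters those that differ meaningfully into the models. The same section makes the primary analysis per-protocol, so the groups compared are no longer protected by randomisation alone and clean baselines matter more. HbA1c also comes from two health systems, so two teams could each follow a different section.

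**Working it through.** The plan gives no HbA1c effect size, standard deviation, number of diabetic patients or power, so there is no figure to reproduce. The check compares the rules, then shows what a late baseline would do under stated assumptions.

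**The rules side by side**

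| | Section 8.2 | Section 9.12 |
|---|---|---|
| Baseline | last value before the baseline assessment | value at the appointment nearest the baseline interview, either side |
| Follow-up | last value in the study period, glossed as nearest 6 months | value at the appointment nearest the 6-month interview, either side |
| Window, tie rule, bar on reuse | none stated | none stated |

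**One hypothetical patient**, with HbA1c at months −4, +3 and +10, all inside the extraction range of −6 to +12.

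- 9.12 baseline: distances to month 0 are 4, 3 and 10, so +3 is chosen.
- 9.12 follow-up: distances to month 6 are 10, 3 and 4, so +3 is chosen again. The change is exactly zero.
- 8.2, reading the study period as the 6 months of participation in 7.1: baseline is −4 and follow-up is +3, which are two different measurements.
- 8.2, if the study period were read as the whole extraction range: the last value is +10, but the value nearest 6 months is still +3. The wording of 8.2 therefore needs a defined period as well.

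**A patient for whom the rules agree.** HbA1c was drawn at the regular visit 1 week before the interview. Both sections take that value unless another was drawn within 1 week after the interview.

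**Illustrative size.** Let f be the share of patients whose baseline value falls t weeks after baseline, and g(t) the fraction of the 26-week effect present by then. With a change score, the fraction of the true arm difference retained is

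retained = 1 − f × g(t).

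Two onset shapes are assumed: linear, g(t) = t/26; and exponential with a 5-week half-life, g(t) = (1 − 2^(−t/5)) / (1 − 2^(−26/5)). For f = 25% and t = 8:

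- linear: 1 − 0.25 × 8/26 = 1 − 0.25 × 0.308 = 0.923
- exponential: g(8) = 0.670/0.973 = 0.689, so 1 − 0.25 × 0.689 = 0.828

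| f | t (weeks) | Retained, linear | Retained, exponential |
|---|---|---|---|
| 0% | any | 100% | 100% |
| 25% | 2 | 98.1% | 93.8% |
| 25% | 8 | 92.3% | 82.8% |
| 50% | 8 | 84.6% | 65.6% |

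Neither f, t nor the onset shape is in the documents. The formula leaves out patients for whom one value serves both time points; each of those contributes a change of zero.

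**The case against.** The strongest reply is that 8.2 is the endpoint definition and already excludes post-baseline values, while 9.12 is a procedural passage explaining why charts are used instead of a blood draw. On that view nothing conflicts: 9.12 names the source and 8.2 the rule. That is a reasonable reading, but the plan does not state it, and whoever abstracts the data is more likely to work from the procedures section.

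The second reply stands. Patients are identified through an upcoming appointment, screened after it and interviewed after it, so the appointment nearest the baseline interview will often be the one just before it. The rules part mainly when HbA1c was not drawn at that visit or the gap to the interview is long. No maximum gap is given.

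Three stronger readings are tempting and are not supported:

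- A reader might infer that the HbA1c result will be shrunk by a known amount. The documents give no share of patients affected. The loss starts at 0%, and without a true effect there is nothing to attenuate.
- A reader might infer that 8.2 freely admits a follow-up value from the first weeks. Its bracket sets the 6-month assessment as the target, so an early value would be used only where nothing nearer exists. That is sparse routine data, not a contradiction.
- A reader might extend the baseline conflict to LDL. The sentence in 9.12 concerns HbA1c only.

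Finally, describing a late value as post-randomisation is an inference from the arm components starting after the baseline interview.

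**Conclusion.** The inconsistency is real: 8.2 requires a pre-baseline HbA1c, 9.12 does not, and no precedence is stated. Followed literally, 9.12 can yield a baseline taken after the intervention began, or one value used at both time points.

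The size is unknown. If a quarter of patients had a baseline value 8 weeks late, the loss would be about 8% (linear onset) to 17% (exponential onset) of a true effect; at 2 weeks it would be about 2% to 6%; if no patient is affected it is zero. All of these rest on assumed shares, timing and onset.

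The point affects one secondary or exploratory outcome in diabetic patients. Hypotheses H1–H4, the primary adherence analysis and the sample size in 11.2 are untouched. Priority: minor. It is worth making because the correction is nearly free and should be settled before the data are analysed.

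**What to change.** Align 9.12 with 8.2 and state one rule in both places:

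- **Baseline:** the last HbA1c on or before the baseline interview, within the 6-month look-back already requested in 9.19.
- **Follow-up:** the post-baseline HbA1c closest to the 6-month assessment, inside one prespecified window. The limits must be reconciled with 8.2's restriction to the study period; a window reaching past 6 months would require 8.2 to be reworded.
- **No reuse:** the follow-up value may never be the baseline value.
- **Analysis:** model follow-up HbA1c adjusted for that baseline value, rather than relying on a raw difference or on baseline HbA1c entering only if the arms look unbalanced.

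Adjustment alone would not cure a late baseline, so the selection rule has to be settled first. The cost is wording: the existing data pull already covers the dates needed. A few patients with no value in the window will become missing and should be counted by arm.
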